This is an fMRI measure of brain function while imagining pain happening to oneself or the virtual counterpart. Following standard preprocessing of fMRI data, we will calculate the regression coefficient for each stimulus type (Self Pain; Self No Pain; Other Pain; Other No Pain). We will extract mean activity from a priori regions-of-interest (ROIs), established as 10-mm radius spheres around MNI coordinate peaks in dACC (-2,33,40) and anterior insula (left: -40,22,0; right: 39,23,-4), which were identified as key regions for pain response in a recent meta-analysis. Brain activity will be quantified by contrasting self-perspective pain (Self Pain vs. Self No Pain) with other-perspective pain (Other Pain vs. Other No Pain). Cohen's d effect size will be calculated separately for each treatment and each ROI. For more traditional statistical measures, a 2x3 (pain perspective condition by group) within-subjects ANOVA test will be performed on data from each ROI.

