12.0 Statistical Considerations

We will enroll 95 children in order to target 40 completers ($n = 20/\text{group}$, allowing for 15-20% screen fail and 15-20% attrition). Attrition (apart from screen fails) will occur between the two scanning visits, which are only one week apart and are expected to be due to noncompliance or in-scanner subject motion that renders data unusable. Attrition rates are not expected to

change from year to year, as subjects will remain active only from the time of screening to Visit 3 (up to 8 weeks).

In similar research, pre/post correlations of 0.72 and 0.89 were found for measures of Theory of Mind (closely related to social perspective taking) in a VR intervention for social cognition training.⁵⁰ In research by co-I [name] involving a multi-session skill-building intervention,⁵¹ pre/post scores had a correlation of 0.69 on the Perspective Taking subscale of the Interpersonal Reactivity Index. Here, we use a more conservative estimate for a pre/post correlation of social perspective taking of 0.6. With 20 subjects per group and assuming an ANCOVA model (specified below) is used with a pre/post correlation for social perspective taking of 0.6 an effect size of 0.73 (observed for the meanness rating in the preliminary study) can be detected between two groups with 80% power using a two-sided two-sample t-test with alpha level of 0.05.

For each primary outcome measure, a separate linear mixed model will be employed to determine predictors of post-treatment scores, with pre-treatment scores, condition, time, group, and a time-by-condition interaction term as regressors. Time-by-condition is a regressor to account for potential improvements in perspective taking with treatment (since there are two conflict scenarios presented). From this model, using appropriate contrast statements we can both test for the primary endpoint (change at end of Scenario 3) and examine trends over time between the three groups. We will also conduct with fMRI data a 2x3 (pain perspective condition by group) within-subjects ANOVA on data from each ROI.

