Across the entire sample, we will calculate the correlation of IRI Perspective Taking with our pre-treatment VR Perspective Taking and AOP scales, to further validate these measures. Similarly, we will assess the relationship between target engagement measures with VC Intentions and Real-life Responses. Exploratory regression analyses will also examine whether target engagement measures are associated with age, sex (to address sex as a biological variable), IQ, task completion, mood, callous-unemotional traits, past experience with video games or VR, or Environmental Presence (each variable examined separately due to the small sample sizes). Finally, we will conduct whole-brain fMRI analysis (2x3 pain perspective condition-by-group ANOVA), in order to identify neural changes in areas outside our primary ROIs (cluster-corrected $p < .05$).

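### The ANOVA for the primary fMRI outcome assumes three within-subjects groups in a two-arm parallel trial, does not say how the Visit 2 scan enters, and is not ranked against the mixed model

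*Combined protocol and SAP*

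**What the plan says.** **The ANOVA.** Section 3.0, on the neural response outcome, states that "a 2x3 (pain perspective condition by group) within-subjects ANOVA test will be performed on data from each ROI". Section 12.0 says the same: "We will also conduct with fMRI data a 2x3 (pain perspective condition by group) within-subjects ANOVA on data from each ROI". The exploratory whole-brain analysis in Section 12.0 is again a "2x3 pain perspective condition-by-group ANOVA", run "in order to identify neural changes in areas outside our primary ROIs".

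**The mixed model.** Section 12.0 also states: "For each primary outcome measure, a separate linear mixed model will be employed to determine predictors of post-treatment scores". The model is specified there "with pre-treatment scores, condition, time, group, and a time-by-condition interaction term as regressors". Its contrasts are meant to "test for the primary endpoint (change at end of Scenario 3) and examine trends over time between the three groups".

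**The design.** Sections 5.0 and 7.0 (Visit 3) allocate each child, in equal numbers, to the alternate perspective or to the control perspective. Section 12.0 targets 40 completers, 20 per group, and its power statement concerns an effect that "can be detected between two groups with 80% power using a two-sided two-sample t-test". The scan is done at Visit 2, before the VR intervention, and repeated in identical form at Visit 3, after it. Section 3.0 defines a post-minus-pre change score for the two VR scales. For fMRI it defines a self-versus-other pain contrast in each region but no change score.

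**The concern.** The fMRI response is a declared primary outcome and the only one that addresses Aim 2. The plan gives it two analyses. One has a factor layout that the trial does not have. The other has terms and an endpoint that do not exist for scans. Nothing says which one governs.

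Changing 3 to 2 repairs the layout but leaves open which scan supplies the data. An analyst could use Visit 3 alone, the Visit 3 minus Visit 2 difference, or Visit 3 adjusted for Visit 2, in each of three regions (dACC, left and right anterior insula). These have different power and can give different answers. If the choice is made after the data are seen, the primary result is no longer fully pre-specified.

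**Working it through.** **Step 1. Number and type of groups.** With 40 completers at 20 per group, 40/20 = 2 groups. A fully within-subjects 2x3 layout has six cells and needs every child in all six. Here each child is in one arm and contributes two cells (Self and Other). Group is therefore between-subjects with two levels, and only perspective is within-subjects. The layout that fits is a 2x2 mixed ANOVA, in which the group-by-perspective test has 1 and 40 − 2 = 38 degrees of freedom.

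**Step 2. What that test is.** For each child let C = (Other Pain − Other No Pain) − (Self Pain − Self No Pain). The group-by-perspective test is the two-sample comparison of mean C between arms. With Visit 3 data only, it contains no baseline information.

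**Step 3. Does the mixed model fit the scans?** Its response is the post-treatment score. Each child has one post-treatment scan, so for C:

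- Time has one level and cannot be separated from the intercept.
- Time-by-condition cannot be separated from condition.
- If time is read as Visit 2 versus Visit 3, the Visit 2 value becomes both a response and a regressor.
- Change at Scenario 3 is defined for the VR scales, not for a scan.
- Condition and group are separate regressors. In the ANOVA text condition means pain perspective; elsewhere (Sections 3.0 and 5.0) it means treatment arm. The model does not say which is meant.

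Without the terms that cannot be estimated, what remains is Visit 3 adjusted for Visit 2, an ordinary ANCOVA. The plan does not say so.

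**Step 4. The plan's own power figure.** Inputs from Section 12.0: n = 20 per group, effect 0.73, pre/post correlation r = 0.6, two-sided alpha 0.05.

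- Residual SD factor: √(1 − 0.6²) = 0.80
- Adjusted effect: 0.73/0.80 = 0.9125
- Noncentrality: 0.9125 × √(20/2) = 2.886
- Power (noncentral t): 0.803 on 38 df, 0.802 on 37 df

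The stated 80% reproduces, and it depends on baseline adjustment.

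**Step 5. With and without the baseline scan.** The documents give no effect size or retest correlation for fMRI. The 0.73 is borrowed from the behavioural calculation and expressed in SDs of the analysed contrast; r is assumed.

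| Analysis | Adjusted effect | df | Power |
|---|---|---|---|
| Visit 3 only | 0.73 | 38 | 0.614 |
| Adjusted, r = 0.3 | 0.73/0.954 = 0.765 | 37 | 0.654 |
| Adjusted, r = 0.4 | 0.73/0.917 = 0.796 | 37 | 0.689 |
| Adjusted, r = 0.5 | 0.73/0.866 = 0.843 | 37 | 0.738 |
| Adjusted, r = 0.6 | 0.73/0.80 = 0.9125 | 37 | 0.802 |

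At 80% power the detectable effect is 0.91 with Visit 3 only, and 0.73 with adjustment at r = 0.6.

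**Step 6. What the self-versus-other contrast can show.** The between-arm effect on C is (effect on Other) − (effect on Self). A rise of δ in Other with no change in Self gives δ. No change in Other with a fall of δ in Self gives 0 − (−δ) = δ. The test alone cannot tell these apart.

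**The case against.** The best defence is that the three-group text is a slip with an obvious repair, and that baseline adjustment is already planned. Much of this stands. Section 12.0 gives every primary outcome a pre-treatment regressor, and a Visit 3-only comparison would still be valid under randomisation. What remains is that the layout is wrong wherever it appears, the model is not adapted to scans, and neither analysis is named primary.

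A reader might go further in four ways that the documents do not support.

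- **That the ANOVA leaves out the baseline scan.** The text refers only to data from each region and does not say which scan enters. The whole-brain aim speaks of neural changes, Section 7.0 allows the Visit 3 scan to be skipped if the Visit 2 scan was not completed successfully, and Section 12.0 places attrition between the two scans. All three are compatible with paired use. The gap is an unstated role for Visit 2.
- **That the fMRI outcome has 61% power.** Section 12.0 makes no fMRI power claim. The figure is illustrative, and at r = 0.3 adjustment adds only about 4 points (0.614 to 0.654).
- **That Aim 2 may be claimed only if the Other response rises.** Section 3.0 declares the self-versus-other contrast, Section 1.0 gives a reason for a Self reference, and nothing in the documents suggests that Self will fall. Such a rule is a trade-off. With a true rise of 0.73 SD in Other, retest correlation 0.3–0.6 and self/other correlation 0.2–0.7, also requiring the confidence interval for Other to lie above zero lowers simulated power from 46–95% to 39–76%.
- **That the fMRI Cohen's d is defined differently from that of the VR scales.** The between-arm definition for those scales ends with similar per-treatment shorthand, so the wording does not show a real difference.

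**Conclusion.** The concern holds for the layout, the fit of the mixed model to the scans, and the ranking. The 2x3 within-subjects ANOVA contradicts the trial's own two-arm parallel design and cannot be run as written. This rests on the text alone and needs no assumption. The plan also leaves unstated how the Visit 2 scan enters the ANOVA, and it names no primary fMRI analysis.

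The baseline question is one of efficiency and pre-specification, not validity. Its size, 61% against 65–80% power, rests on a borrowed effect of 0.73 SD and an assumed retest correlation of 0.3–0.6. The ambiguity between a rise in Other and a fall in Self is a matter for reporting, not an error in the declared contrast.

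**What to change.** Required, in Sections 3.0 and 12.0:

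1. Replace 2x3 with two groups in both region-of-interest statements and in the whole-brain analysis, and correct the reference to three groups. State that group is between-subjects and perspective within-subjects.
2. Name one primary fMRI analysis for each region: the declared self-versus-other contrast at Visit 3, compared between arms and adjusted for the same contrast at Visit 2. If the ANOVA is kept, call it supportive and say which scan or scans it uses.
3. Limit the Scenario 3 endpoint and the time terms to the two VR scales.

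Optional: report the baseline-adjusted between-arm effect on (Other Pain − Other No Pain) with its 95% confidence interval, so that readers can see which response moved. It need not be a condition for the Aim 2 claim.

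The cost is wording and one degree of freedom per region model (38 to 37). Both scans and all four stimulus coefficients are already planned.

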4.0 Eligibility Criteria

4.1 Inclusion Criteria

Children:

- Aged 9-12 at time of enrollment
- English-speaking
- Meet DSM-5 criteria for oppositional defiant disorder (ODD), conduct disorder (CD), or Other Specified or Unspecified Disruptive, Impulse-Control, and Conduct Disorder
- Right-handed
- Estimated full-scale IQ greater than 70

Parents/Guardians:

- English-speaking
- Must live with child participant
- Reliable reporter of child's personality and behavior

[figure not shown]
4.2 Exclusion Criteria

Children:

- Bipolar disorder, any disorder involving psychosis, pervasive developmental disorders, current or past substance use disorder, or current major depressive disorder
- History of neurological problems (e.g., epilepsy, traumatic brain injury)
- Contraindications for MRI
- Sibling who has participated in this study
- Experience negative side effects during use of virtual reality (e.g., VR sickness)
- In opinion of investigator, cannot complete study procedures or is inappropriate for study participation

5.0 Study Design

This project will examine how levels of a virtual reality treatment that provides users with the alternate perspective of an interpersonal interaction impacts psychological and neurobiological markers of perspective taking. Prior to Visit 3, participants will be randomly assigned to different VR perspective conditions, stratified by sex, presence/absence of ADHD diagnosis, and ODD/CD diagnosis, via an a priori randomization chart. An equal number of youth will be randomly assigned to either the alternate perspective condition or control condition. Assignment will be sealed for the experimenter until immediately prior to Visit 3 (for visit preparation, experimenter must be unblinded). Visits 1 and 2 will be identical for both groups. At Visit 3, the initial VR scenarios and assessments will be identical. The participant will then re-experience the VR scenarios depending on their assigned condition. Additional VR assessments and the MRI scan will be identical for both groups.

6.0 Recruitment & Enrollment/Randomization

Participants will be recruited in a variety of manners, including direct contact and flyers at the Riley Child and Adolescent Psychiatry Clinic (RCAPC) and Eskenazi Health, print and radio advertisements, community flyers, work with local organizations, and potential contact through recruitment services and health databases.

At the RCAPC, all clinical psychologists, psychiatrists, and social workers at the clinic will be informed of the study and provided informational flyers for patients, which will also be posted in the waiting room. The same will occur at Eskenazi Health. Providers may also post a brief description of the study along with our contact information, links to our lab Facebook page and REDCap landing page (described below), and a QR code linked to our REDCap Landing Page in their virtual waiting rooms seen by patients waiting for their remote visits to begin.

We will also recruit subjects from a medical records review with information provided to us by the IU Health Research Data Extraction process. The IU Health Information team will evaluate the medical records from the RCAPC and provide our study team the general information (name, MRN#, birthdate, date of diagnosis, etc.) and contact information of patients who meet our study's inclusion and exclusion criteria. Once provided with a list of children who may match our study's qualifications, we will reach out to parents via the contact information provided to describe our study and gauge their interest in participating, through a postcard mailed to their address and then follow-up with phone calls or emails, or via direct email contact.

Paper flyers will also be posted in public arenas around the Indianapolis area, including libraries, bus stops, coffee shops, and other community boards. Flyers may also be posted in IUPUI and IU Health facilities, or additional local child mental health facilities where permission has been provided. Flyers will also be provided to current subjects who indicate an interest in providing information to other interested subjects. We will also contact local organizations, including local schools and summer camps. Potential participants and parents will be asked to email or call our recruitment-designated email address and/or phone number.

We may partner with community organizations who may post information about our study on their social media sites (Facebook, Instagram, Twitter, etc.). These posts may include study details, pertinent inclusion/exclusion information, study contact information including our recruitment website, and will not emphasize payment for participation. Partner organizations may also provide contact information of potentially interested parties. The research team can then initiate contact with potential subjects to gauge their interest in participating in our study.

We will also recruit parents/guardians of potential participants via study information provided to the All IN for Health Research and Clinical Studies database (<https://allin4health.info/>) and the ResearchMatch database (<https://www.researchmatch.org/>). The All IN for Health Research and Clinical Studies database is powered by TrialX iConnect and provides a list of active studies being conducted in Indiana by faculty at Indiana University and other research institutions in the surrounding area. Anyone can browse studies by location, keywords, health topics, or conditions and directly contact the study team. ResearchMatch is a similar database, although national in scope. Another aspect of the All IN for Health database and ResearchMatch is their volunteer registry. Researchers can browse users who have agreed to input their medical history, and request to contact those who might match the qualifications for our study. Some study flyers will also include a QR code directing participants to our information on these sites.

Study information will be included in the iConnect All IN for Health e-updates newsletter, emailed bi-monthly to more than 32,000 subscribers which includes those in the All IN for Health volunteer database. The newsletter shares what's going on in the community to improve Indiana health. Study information will also be posted from the iConnect social media accounts (Facebook, Instagram, Twitter, etc.).

A study posting with a brief description of the study will also be sent to IUHealth News, which is sent to all IUHealth employees.

We will post study information to online community boards, such as craigslist.org, nuvo.net, IU classified pages, and similar sites.

Information about the study and a link to our All IN For Health page and our REDCap landing page will also be posted on our lab website, on our lab Facebook page, and on the IU School of Medicine Facebook page. Members of the study team may also share or post information about the study on their personal social media sites. This information will note that the study is paid but will not include specific payment information (e.g., dollar amounts).

We will also recruit parents/guardians of potential participants via social media. We will run Facebook ads from our lab account and from the IUSM account that show information about the study to targeted Facebook users. Our target user will be adults in Indianapolis with children ages 9 – 12. If a user would like more information and clicks on the post, they will be directed to one of two places: either our study's All IN for Health Research and Clinical Studies website where there is an opportunity to contact the study team directly, or to our REDCap landing page where there's an opportunity to answer some brief eligibility questions then contact the study team. The REDCap page will ask broad, preliminary questions related to study criteria, but these responses will not be used to assess eligibility. We will reach out to individuals who provide contact information via the REDCap page, in order to provide additional study information.

IndyVRstudy.com is our study website that displays information about the study (what's involved, who is eligible, etc.) and information about the research team (contact info, link to our lab Facebook page). There are also multiple buttons that redirect visitors to our REDCap landing page for additional information. The site will be used with word-of-mouth recruitment, on social media posts, and with other recruitment materials as study contact information.

Parents and children will also be recruited via an online blog post by the Indy's Child magazine. This blog post will include information about the study and links to the lab Facebook page as well as the All IN For Health page. If interested, potential subjects will be able to enter their information via All IN For Health. This blog post will target our specific demographic of parents in the Indianapolis area.

We will also use on-air radio and tv commercials to recruit potential subjects. This ad will briefly describe the study, potentially mention compensation, and direct those interested to reach out by phone or email or to visit our recruitment website (IndyVRstudy.com).

Digital ads containing a brief description of the study with a hyperlink to our recruitment website will be displayed on the WFYI website, as well as sent out in e-newsletters to WFYI subscribers.

We will also run a people-based marketing campaign. Digital ads such as emails, social media, website banner ads etc. will be presented to parents and teachers in the Indianapolis area who voluntarily submitted their information to a media habit database managed by Cumulus Media. The research team does not have access to this database and will only learn identifying information of those included in the campaign audience if one chooses to express interest in the research via phone, email, All IN for Health or REDCap Landing Page.

If a parent expresses interest in the study via phone or email, we will contact them via phone to describe the study and ensure the child meets inclusion/exclusion criteria. We will ask them

screening questions derived from DSM-5 criteria for oppositional defiant disorder, as well as excluded disorders (e.g., neurodevelopmental disorders, current depression). If they potentially qualify via review by the PI and clinical co-Is, they will be scheduled for their screening session. We will send directions and informed consent and assent forms for them to review (these will be reviewed and signed in person). We will provide reminder contacts (email or phone, as preferred) at least one week prior to their session date.

Participants may also opt-in to text reminders about study visits. When scheduling the first visit, we will ask questions whether they want to be texted from our Google Voice account. We will note that messages will only be sent from lab-issued devices and we will delete all contacts and contact info from devices following completion of their participation. However, Google Voice may maintain a call history with the account.

All text messages will be sent from our Google Voice number via the lab tablets. These tablets are password-protected, and any contacts with study participants made via the Google Voice account, including texts and contact info, will be deleted upon completion of the subject's participation.

Participants will be instructed that if they need to contact the study team on the day of their study visit (e.g., if they are running late), to call or text us via our Google Voice number, which can be connected to our lab tablets.

For Visit 3, we will remind parents of the information they completed on the Medication Log (see Visit 2 Study Procedures), as it would be helpful for the same medications to be used at that visit. However, we will caution that they should use their best judgement and follow doctor's orders when providing medication, and that this is not a study requirement.

Randomization will occur only for those participants that meet all inclusion/exclusion criteria following the first study visit and are able to be scheduled. A randomization table will be created by our statistical team, stratified by sex, ADHD status, and ODD/CD diagnosis to create equal numbers of boys and girls in each condition. This assignment will be sealed to the research team until within 24 hours of the third study visit.

Previously active subjects whose visits were cancelled due to the COVID-19 outbreak will be permitted to restart all study procedures, including being reconsented using the most recent informed consent documents.

